Records include patient’s medical record numbers, demographic characteristics, diagnoses (code and encounter date), inpatient and outpatient encounters, and other medical care. Approximately 65 (5 for the open pilot, 60 for the RCT) participants meeting these criteria will be identified and recruited. We will exclude participants who: (1) do not speak English, (2) do not have health insurance, (3) are under the age of 18, (4) are over the age of 65, (5) are unable to give informed consent due to psychiatric, cognitive, or medical (ie. Patient in hospice at end of life) impairment as determined in consultation with study PI, patient navigator, or oncology social worker, and (6) do not have access to a smartphone, computer or tablet with internet access. The rationale for the third exclusion criterion is that an intervention with a large number of Medicaid-eligible survivors would be outside the scope of the current intervention. The rationale for the fifth exclusion criterion is that the health insurance navigation intervention is delivered via an MGB-approved video-conferencing system (ie. Zoom).

A member of the research team will review the electronic medical record (i.e., EPIC) to ensure that identified patients are eligible for the study before proceeding with outreach. A team member will confirm that the patient is alive and has not been hospitalized within the past year due to psychiatric reasons.

Sources of Subjects and Recruitment Methods

The Research Patient Data Registry is a centralized clinical data registry that stores and gathers patient information from across the Mass General Brigham system. It provides clinical researchers the ability to perform population queries and identify target subpopulations for research studies. Research Options Direct to You [RODY] patients and self-referred within the RDPR will be contacted about the study.

5. Subject Enrollment

Methods of Enrollment

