Potential participants will be identified via the Mass General Brigham RDPR. Patients among the Research Options Direct to You (RODY) designation within the RDPR will receive an opt-out letter from the study team. This letter (See Recruitment Letters) will describe the study procedures and ask patients to contact the study team within 3 days if they would not like to be contacted further about the study. Those who do not opt-out will be contacted via encrypted email or by phone by the PI or by a trained and CITI-certified research staff member, and they will be read or sent a brief description of the study (See Study Description Documents).

Patients may also express interest in the study by contacting the research team directly.

Patients who are interested will be screened for eligibility, and those who are eligible will undergo informed consent. Specifically, eligible and interested patients will be asked to review the study fact sheet by phone with a study team member. Once that is completed, the study fact sheet will be sent to participants in an encrypted / unencrypted email, depending on their preference (see HINT C Short Consent). This method of obtaining consent has been used in other IRB-approved trials, like 2018P000539). Following consent, enrollees will be assigned a unique study identification number and will complete a baseline assessment. Patients who consent and complete the baseline assessment will then be randomized into the intervention or control arm.

The study interventionist will contact consented participants randomized to the intervention via unencrypted or encrypted email to schedule the HINT sessions, again depending on patient preference. To facilitate communication with the oncology team, the interventionist will complete a summary documentation note within EPIC informing clinicians of the patients' participation in the program. We will send reminder notices via calls, emails, mail, and Patient Gateway for participants who have not completed the baseline survey or for those in the intervention arm who have not scheduled their sessions, as needed (see "HINT C Difficult to Reach Letter").

Privacy protection: To address security issues related to email communication, participants will be informed about security in the opt-out letter itself via inclusion of the following text:

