"Please note that emails sent to the study staff from your personal email address may not be secure and could result in the unauthorized use or disclosure of your information. If you want to email the study team despite these risks, Partners HealthCare will not be held responsible. If you do not want to email the study team, you may instead call [XXX RA's phone number]".

For any emails sent by the study team, they will be encrypted using Send Secure unless patients verbally agree to receive unencrypted email, which we will document. Patients will receive the following information:

"The Partners HealthCare standard is to send email securely. This requires you to initially set up and activate an account with a password. You can then use the password to access secure emails sent to you from Partners HealthCare. If you prefer, we can send you "unencrypted" email that is not secure and could result in the unauthorized use or disclosure of your information. If you want to receive communications by unencrypted email despite these risks, Partners HealthCare will not be held responsible. Your preference to receive unencrypted email will apply to research studies for emails sent to you from research staff in this study. If you wish to communicate with other research staff at Partners regarding additional studies, your preference will have to be documented with each research group."

Informed Consent

Eligible and interested patients will be asked to review the study fact sheet by phone with a study team member. Once that is completed, the study fact sheet will be sent to participants in an encrypted / unencrypted email, depending on their preference (see HINT C Short Consent). This method of obtaining consent has been used in other IRB-approved trials, like 2018P000539).

Intervention Assignment and Randomization

Using the RDPR, MGH staff will outreach to patients meeting the eligibility criteria and query terms. For the randomized pilot trial, the 60 participants will be randomized to either enhanced usual care (n=40), or the health insurance navigation intervention (n=40). Randomization will employ a random plan generator, with consented patients being randomly assigned to either the enhanced usual care or the health insurance navigation intervention, stratified by age (18-39 and 40-65).

6. Study Procedures

Navigation Intervention

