The patient navigator (PN) will undergo training by the Co-investigators and pilot sessions. The NCI, with support from the ACS, established the Patient Navigation Research Program (PNRP) to implement and evaluate patient navigator programs. The PNRP developed a navigation performance checklist with 3 quality indicators of care:^{17,18} 1) participant interaction (e.g., established rapport), 2) care management (assessed subjects' understanding), and 3) intervention delivery (e.g., relevant information provided on insurance options, cost savings). Study investigators will review approximately 15% of patient navigation encounters using these quality indicator criteria. Navigation sessions will be recorded following patient assent to facilitate these fidelity assessments. The recordings will be audio and not video.

Measures

To evaluate the pilot, we will use a mixed methods data collection approach, using both quantitative survey items and open-ended questions.²⁶ Most study measures will come from survey questions repeated from the 2011-2012 CCSS health insurance survey (see Appendix); some new questions will be added and are indicated as such. Survey development included modifications and inclusions of national survey questions²⁶⁻³² and a cognitive testing phase. Using data collected previously by the RDPR via abstraction of medical records, data will be used to provide information on cancer diagnosis, age at diagnosis, and cancer treatment. Data from the RDPR will provide information on sociodemographic and medical history since cancer treatment, and presence of a medical late effects and chronic health conditions including second cancers. The measures will include the following:

Participant Characteristic Measures (From RPDR and/or study surveys)

Characteristics: Age, Gender, Education, Race/Ethnicity, Partnership/Marital Status

Enabling Characteristics: Zip Code, Familiarity with ACA Policies

Health Insurance Literacy: Likert scale assessments of- Confidence in Understanding of Terms (e.g. Coinsurance), Confidence in Choosing, Comparing, and Using Insurance, Household and Personal Income

Cancer Diagnosis, Treatment Type

Outcome Measures

Primary Outcomes: Feasibility and Acceptability.

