The consent form states that there may be no direct benefit to the participants from study participation. Participants in both groups will be given information that could improve their ability to access affordable coverage. Participants in the intervention group will also receive navigation support, for up to 5 video-based sessions. As an alternative to the intervention, participants may explore health insurance support options at their current primary care center.

9. Statistical Analysis

[name], and the study team at University of Utah will complete the analyses. The team will be blinded to treatment allocation until trial analyses completion. [name] team will receive de-identified study data.

Open Pilot

Pilot data is meant to inform and test the function of the study procedures, so no formal analyses will be performed. We will use preliminary feasibility and acceptability data (as outlined below) to inform necessary changes to our approach.

Randomized Trial

Quantitative Data

We will use descriptive statistics to report on the following endpoints: intervention feasibility (percent of participants enrolled), acceptability (satisfaction, perceived support) and efficacy (e.g., ACA familiarity, health insurance literacy, intention to adhere to recommended survivorship care, provider communication, and coverage status). Descriptive statistics will examine group differences at baseline; any imbalances will be adjusted. We will use chi square and independent t-tests to compare end-of-intervention changes in preliminary efficacy outcomes between the two groups. Although a 3-month post intervention follow-up period is brief, we will also conduct exploratory comparisons with other study outcomes to see if trends change in the expected direction. We will compare pre/end-of-treatment, within groups, with paired t-tests. In addition, we will use bivariate statistics to examine sociodemographic and cancer-related factors (e.g., type of diagnosis, age at diagnosis, cancer treatment¹⁸, cancer treatment (e.g., cranial radiation yes/no, anthracycline exposure yes/no) associated with feasibility, acceptability and preliminary efficacy outcomes.

10. Monitoring and Quality Assurance

Training of all Study Personnel in the Responsible Conduct of Human Studies

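### The between-arm efficacy tests do not condition on the baseline value, and adjustment is left to observed imbalances with no rule

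*Combined protocol and SAP*

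**What the plan says.** The between-arm efficacy analysis is one sentence in Section 9 (Randomized Trial, Quantitative Data): "We will use chi square and independent t-tests to compare end-of-intervention changes in preliminary efficacy outcomes between the two groups". The sentence before it is the only mention of adjustment: "Descriptive statistics will examine group differences at baseline; any imbalances will be adjusted". No section says which variables are examined, how large a difference counts as an imbalance, or what model does the adjusting. The other analyses in Section 9 are paired t-tests within each arm and bivariate associations, and neither adjusts the arm comparison.

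The data for a baseline-conditioned analysis will exist. Section 5 (Methods of Enrollment) says "Patients who consent and complete the baseline assessment will then be randomized into the intervention or control arm". Section 5 (Intervention Assignment and Randomization) describes allocation as "stratified by age (18-39 and 40-65"), but Section 9 does not mention the strata.

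Section 6 (Measures) lists one of the two Aim 2b outcomes among the participant characteristics: "Health Insurance Literacy: Likert scale assessments of- Confidence in Understanding of Terms". Financial distress, the other Aim 2b outcome, is not in that list. Section 9 also says of the analysts: "The team will be blinded to treatment allocation until trial analyses completion".

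**The concern.** A change score fixes the coefficient of the baseline value at 1. ANCOVA estimates that coefficient, and when the two SDs are equal it is never the less precise method apart from the degree of freedom spent. The t-test and chi-square test that the plan names cannot take a covariate, so the promised adjustment cannot be carried out with the analysis as stated. It needs a model that the plan does not give.

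Two things are at stake. One is precision in a small trial. The other is that the covariate set will depend on the observed baseline table and on a threshold that nobody has written down, so a second statistician could not reproduce the analysis from the text. It is also unclear whether the baseline value of the outcome is among the variables to be checked, above all for financial distress.

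This matters mainly for health insurance literacy and financial distress, which carry a directional hypothesis in Aim 2b.

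**Working it through.** **Inputs from the documents.** About 60 are randomized, which is 30 per arm if the arms are equal. Sections 3 and 5 also give 40 per arm, which sums to 80, so both sizes are shown. There is one baseline survey and one follow-up survey. The plan gives no power figure to reproduce, and no alpha, SD, effect size, dropout rate or baseline to follow-up correlation.

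**Assumptions.** Two-sided alpha 0.05; effect 0.6 baseline SD; correlation r from 0.3 to 0.8; bivariate normal scores.

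**Step 1: variances.** Take baseline SD 1 and follow-up SD k.

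- Change score: 1 + k² − 2kr.
- ANCOVA residual: k²(1 − r²).
- With k = 1 these are 2(1 − r) and 1 − r², so the ratio of ANCOVA to change-score variance is (1 + r)/2: 0.65, 0.75, 0.85 and 0.90 at r = 0.3, 0.5, 0.7 and 0.8. At r = 0.5, ANCOVA on 60 × 0.75 = 45 people would match the change-score test on 60.
- With k = 1.25 the ratios are 1.422/1.8125 = 0.78, 1.172/1.3125 = 0.89, 0.797/0.8125 = 0.98 and 0.5625/0.5625 = 1.00. The advantage is gone when kr = 1, because the ANCOVA slope is then itself 1.

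**Step 2: closed-form power at 30 per arm, k = 1.** The noncentrality parameter is 0.6/(SD × √(2/30)), with √(2/30) = 0.258. Change score against ANCOVA: 49% vs 67% (r = 0.3), 63% vs 75% (0.5), 84% vs 89% (0.7), 95% vs 97% (0.8).

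**Step 3: simulation of the plan's conditional adjustment.** There were 40,000 runs per cell, with 25% in the younger stratum and no age effect. The plan is taken as a change-score t-test that switches to ANCOVA (arm, baseline value, age stratum; 2n − 4 degrees of freedom) when the baseline difference in the outcome passes a trigger. Power at 30 per arm, k = 1:

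| r | Never adjusted | p<0.05 | >0.25 SD | >0.10 SD | ANCOVA always |
|---|---|---|---|---|---|
| 0.3 | 49% | 50% | 54% | 60% | 66% |
| 0.5 | 63% | 64% | 67% | 71% | 74% |
| 0.7 | 84% | 84% | 86% | 88% | 89% |
| 0.8 | 95% | 95% | 96% | 96% | 96% |

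Simulated ANCOVA is up to 1 point below the closed form because the slope is estimated. Type I error is 4.9-5.2% for either fixed method and 3.3-4.7% under a trigger, which is mildly conservative. The mean 95% CI half-width, from never adjusted to the 0.10 SD trigger, against ANCOVA, is 0.61-0.53 vs 0.50 SD (r = 0.3), 0.51-0.47 vs 0.45 (0.5) and 0.33-0.32 vs 0.31 (0.8).

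**Step 4: sensitivity.** Each range runs from never adjusted to the 0.10 SD trigger, against ANCOVA.

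| Setting | r = 0.3 | r = 0.5 | r = 0.7 |
|---|---|---|---|
| 24 per arm (assumed 20% loss) | 41-51% vs 56% | 53-61% vs 64% | 75-80% vs 81% |
| 40 per arm | 61-73% vs 79% | 76-83% vs 86% | 93-95% vs 96% |
| 30 per arm, k = 1.25 | 40-45% vs 48% | 52-54% vs 55% | 72% vs 72% |

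With k = 1.25 and r = 0.8 the figures are 86-87% vs 86%.

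**Step 5: dependence on the missing rule.** At 30 per arm the SE of a baseline difference is 0.258 SD. The chance of exceeding 0.25 SD is 2(1 − Φ(0.25/0.258)) = 0.333, and of exceeding 0.10 SD it is 0.699. If 10 characteristics were checked (assumed; Section 6 lists about a dozen), the expected number flagged by chance is 10 × 0.05 = 0.5, 10 × 0.333 = 3.3 or 10 × 0.699 = 7.0, depending only on the rule chosen.

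**The case against.** A change-score t-test in a randomized trial is valid and does use the baseline value. Efficacy is secondary and preliminary in Sections 6 and 9, Section 3 sizes the trial for feasibility and acceptability, and no power target is stated that could be missed. All of this stands, and it makes the point one of efficiency and prespecification.

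The adjustment sentence may well cover baseline literacy, since literacy is among the listed characteristics. Even so, adjustment that depends on a trigger recovers only part of the loss (Step 3), and financial distress remains uncertain.

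Blinding of the analysts limits steering toward one arm. It does not name the covariates or restore precision.

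The gain rests on assumed values and can be nil. That is correct, and the range is shown. The documents also give no scoring for financial distress, so the ANCOVA recommendation is conditional on a continuous score. The 0.10 SD threshold is the extreme end of an assumed range, and an SD rule does not transfer directly to categorical characteristics, so the count of 7.0 is only an upper illustration. The age term adds little that can be quantified, because the simulation gives age no effect. None of this supplies the missing rule or model.

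**Conclusion.** The concern holds. Section 9 names no baseline-conditioned model, no covariate and no imbalance rule, and nothing elsewhere in the document supplies one. That conclusion rests on the text alone.

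The size rests on assumptions. With equal SDs and 30 per arm, prespecified ANCOVA gains 17 points of power over never adjusting at r = 0.3 (66 − 49), 11 at r = 0.5 (74 − 63) and about 1 at r = 0.8. It gains 6, 3 and almost nothing over the most liberal trigger. There is no gain at r of 0.7 or more if the follow-up SD is 1.25 times the baseline SD. The efficacy tests are not invalid and no inflation of type I error is claimed. The change is worth making because it costs almost nothing and also fixes the covariate set in advance.

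**What to change.** In Section 9, make three changes.

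1. **Outcomes scored as continuous** (health insurance literacy, and financial distress if it is so scored): prespecify ANCOVA of the value at the 3-month post-program survey on arm, the baseline value of that outcome and age stratum (18-39, 40-65). Report the adjusted difference with its 95% CI.
2. **Binary outcomes:** use an age-stratified test, or an exact test if events are sparse. Add baseline status as a stratum or covariate where it is measured and varies. Insurance status does not vary at baseline, because Section 4 says "We will exclude participants who: (1) do not speak English, (2) do not have health insurance".
3. **Adjustment sentence:** replace it with these named covariates, label any further adjustment a sensitivity analysis, and keep the baseline table descriptive.

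The cost is a few sentences and two degrees of freedom (baseline value and age stratum). No new data are needed, and neither the design nor the sample size changes.

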Health care reform under the Patient Protection and Affordable Care Act (ACA) offers considerable opportunities for colorectal cancer survivors to obtain coverage and improve access to needed care. However, in the general population, many people have low understanding of available insurance benefits and resources and have limited health insurance literacy (i.e. perceived knowledge, ability, and confidence to make informed decisions about choosing and using health insurance).¹⁵ Misperceptions about which services require out-of-pocket costs may lead some enrollees to avoid services that are in fact exempt from cost sharing. For colorectal cancer survivors are particularly vulnerable to financial burden related to low health insurance literacy.¹⁴ For colorectal cancer survivors, having a proficient understanding of health insurance is necessary for obtaining adequate health insurance to meet follow-up and surveillance needs without experiencing a significant degree of financial burden

2. Specific Aims and Objectives

Aim 1: To conduct an open pilot of a videoconferencing-based randomized trial of the health insurance navigation tools program with approximately 5 colorectal cancer survivors.

A1a: To assess the preliminary feasibility and acceptability of the HINT intervention via the measures and methods described below

A1b: To utilize open pilot feasibility and acceptability data to inform Aim 2 (RCT) methodology

Aim 2: To conduct a videoconferencing-based randomized trial of the health insurance navigation tools program (HINT) (n= approximately 60).

A2a: To assess the feasibility (number of eligible enrolled and sessions completed) and acceptability (satisfaction, perceived support) of participants undergoing a health insurance navigation tools program (HINT).

A2b: At 3-month post-program follow-up, to assess the efficacy of the HINT to assist participants with accessing and utilizing coverage and managing costs. Primary outcomes are 1) health insurance literacy and 2) financial distress related to medical costs. A2b Hypothesis: The HINT, compared to enhanced usual care, will improve participants’ health insurance literacy and decrease financial distress.

3. General Description of Study Design

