Open Pilot Design: We will recruit approximately 5 colorectal cancer survivors from Massachusetts General Hospital via the Research Patient Data Registry (RDPDR) to take part in a health insurance navigation intervention. Recruitment, consent, and intervention approach for the pilot will mirror the trial design, as described below. The purpose of the open pilot is to inform any changes in the trial and program approach prior to implementing the randomized pilot trial.

Randomized Trial Design: We will recruit and randomize approximately 60 colorectal cancer survivors from Massachusetts General Hospital via the Research Patient Data Registry (RDPR) to a health insurance navigation intervention or to enhanced usual care (Please see Sections III and IV for information on subject selection and consenting procedures). We have selected this sample size of approximately 40 per arm to enable evaluation of feasibility and acceptability goals as well as explore meaningful differences in the outcomes.⁷⁸ Surveys will be conducted at baseline and 3-month post program completion follow-up via REDCap or mail. All participants will be asked to complete a follow-up survey approximately 3-months after the HINT intervention period (in other words approximately 5-months post pilot trial enrollment). Participants will be remunerated \$20 for each survey.

Study Arms

Enhanced Usual Care

Enhanced usual care will consist of a mailed or emailed copy of a health insurance booklet.

Navigation Intervention

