1. Feasibility: Number of eligible enrollees and number of sessions completed. 2. Acceptability: 4-point scales of satisfaction with navigation services (To what extent has this program met your needs? Did you get the kind of health insurance assistance that you wanted? How helpful has this program been for you?) and perceived support (emotional/informational scale of the Medical Outcomes Study social support survey, an 8-item scale widely used with cancer patients).²⁰⁻²⁴

Secondary Outcomes: Efficacy.

The ACS's National Patient Navigator Leadership Summit recommend patient-navigation outcome measures, which include: perceived knowledge, perceived confidence in overcoming barriers to care, and satisfaction with patient navigation services. Accordingly, we will measure: 1) health insurance literacy, 2) financial distress related to medical costs, 3) familiarity with healthcare reform policies, 4) insurance status (among those insured at study enrollment), and 5) discussion with providers about health care costs²⁴ and preventive services among those having a visit during this interval (2-item y/n questions).

Secondary Outcomes: Program Satisfaction.

Program satisfaction outcomes will include Likert scale (very poor, poor, average, good, excellent) on items including communication with the navigator, scheduling convenience, number of sessions, length of sessions, the health insurance booklet, the overall quality of the program. Satisfaction with the virtual format delivery of the program will also be assessed on a Likert scale, and will include items on the MGB-approved video-conferencing system (ie. Zoom) and the material presented via PowerPoint during the navigation sessions. We will also assess likelihood of program recommendation for other colorectal cancer survivors (definitely would recommend, probably would recommend, neutral, probably would not recommend, definitely would not recommend). Program helpfulness will be assessed on a 1-10 scale. Lastly, open ended questions will be asked about helpfulness of the program and aspects of improve upon. Program satisfaction questions will be asked only of intervention arm participants.

7. Risks and Discomforts

Psychological Risks

Individuals may find it stressful to answer questions about their experiences with health insurance coverage and care. The risks associated with these discussions are minimal, and do not rise above the level of harm encountered during daily activities.

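### Do the Section 9 tests refer to an end-of-programme time point at which no survey is taken?

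*Combined protocol and SAP*

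**What the plan says.** Section 9 (Randomized Trial, Quantitative Data) names the tests and the changes they apply to. Between arms: "We will use chi square and independent t-tests to compare end-of-intervention changes in preliminary efficacy outcomes between the two groups". Within arms: "We will compare pre/end-of-treatment, within groups, with paired t-tests". Between these two sentences stands a third: "Although a 3-month post intervention follow-up period is brief, we will also conduct exploratory comparisons with other study outcomes".

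The survey schedule is in Section 3: "Surveys will be conducted at baseline and 3-month post program completion follow-up via REDCap or mail". Section 3 then dates the follow-up survey for all participants as about "3-months after the HINT intervention period (in other words approximately 5-months post pilot trial enrollment"). Section 6 (Assessments) repeats the two-survey schedule.

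The efficacy aim, A2b in Section 2, sets its own time point: "At 3-month post-program follow-up, to assess the efficacy of the HINT to assist participants with accessing and utilizing coverage and managing costs". It also names its outcomes: "Primary outcomes are 1) health insurance literacy and 2) financial distress related to medical costs". Section 6 (Secondary Outcomes: Efficacy) lists the same two first: "Accordingly, we will measure: 1) health insurance literacy, 2) financial distress related to medical costs".

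**The concern.** The tests in Section 9 are tied to the end of the intervention, but efficacy data are collected only at baseline and about 3 months after the programme. The sentence on the 3-month period adds to the doubt. It can be read as setting up two time points, with formal tests at programme end and exploratory work at 3 months. On that reading the A2b comparison has no assigned test, and the tests that are assigned have no data. A result labelled end-of-intervention could also be taken as an immediate effect when it describes what remained about 3 months later.

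A smaller worry concerns the date of the follow-up survey. Section 6 counts it from programme completion. Controls receive only a booklet and have no completion date, and neither do intervention participants who stop before the fifth session. If the arms were surveyed at different times since enrolment, the comparison would be less clean.

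**Working it through.** **1. Which change scores can be computed?** No arithmetic is needed here, only a count of the scheduled surveys.

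| Time point | Efficacy survey scheduled? | Source |
|---|---|---|
| Baseline | Yes | Sections 3 and 6 |
| End of the sessions | No | none |
| About 3 months after the programme | Yes | Sections 3 and 6; the A2b time point in Section 2 |

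Two surveys give one change per outcome, baseline to follow-up. A phrase in Section 6 (Quantitative Data) puts follow-up surveys in the plural, but it names no second time point, and the same section describes a single follow-up survey. Section 6 does not say when the programme satisfaction items are asked. Those items go to the intervention arm only, so they could not support a comparison between arms. An analyst therefore has one dataset to which the chi-square, independent t and paired t-tests can be applied, and it is the A2b dataset.

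**2. Do the two ways of dating the survey conflict?** Inputs: 3 months after the programme and 5 months after enrolment (Section 3); five sessions every week or two over about one month (Section 3, Navigation Intervention).

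- One month = 365.25 / 12 / 7 = 4.348 weeks, so 3 months = 13.04 weeks and 5 months = 21.74 weeks.
- The two dates coincide when the programme ends 21.74 − 13.04 = 8.70 weeks after enrolment.
- Five sessions have four intervals: 4 weeks if weekly, 8 weeks if every other week. The stated one month is 4.35 weeks.
- Lag from enrolment to first session needed for agreement = 8.70 − span: 4.70 weeks (weekly), 4.35 weeks (one month), 0.70 weeks (every other week).

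The documents give no lag, so these are the values agreement would need and not known facts. They are plausible. The baseline survey, randomisation, contact by the navigator and scheduling all come between consent and the first session, and Section 5 plans reminders for participants who have not booked. Both dates are also stated as approximate.

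**3. Would dating the survey strictly from enrolment be better?** Let L be the assumed lag in weeks, taken from 0 to 4. Programme end then falls between 4 + 0 = 4 and 8 + 4 = 12 weeks after enrolment.

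| Rule | Quantity left to vary | Weekly, L = 0 | Every other week, L = 4 |
|---|---|---|---|
| Fixed at 5 months from enrolment | Weeks since last session = 21.74 − span − L | 17.74 | 9.74 |
| Fixed at 3 months from completion | Weeks since enrolment = span + L + 13.04 | 17.04 | 25.04 |

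Against 13.04 weeks, 17.74 is 4.70 longer (+36%) and 9.74 is 3.30 shorter (−25%). With L = 8 and sessions every other week, the interval falls to 21.74 − 8 − 8 = 5.74 weeks. Under either rule the spread over L = 0 to 4 is 8 weeks (17.74 − 9.74, or 25.04 − 17.04). The choice of rule decides only which interval varies.

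**The case for a change.** The strongest case for an edit is that an analysis section should stand without inference. Nothing in the protocol defines end-of-intervention as the 3-month survey, and Section 9 never says that its between-arm test is the A2b test. The analysis is to be done by a team at another university on de-identified data, and Section 10 plans interim results for annual progress reports, so a loose label could travel into a report. A2b also calls health insurance literacy and financial distress primary outcomes, which raises the standard for stating their test.

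The mismatch in wording is real, and that part of the case stands. What does not follow is any effect on the analysis. The outside team will receive one baseline and one follow-up record per participant and cannot compute a programme-end change. The 3-month sentence also has a natural reading that fits the schedule: its contrast is between outcomes, and it mentions the follow-up period as a known feature of the trial. The risk of mislabelling is met by ordinary reporting practice, which dates a result by the survey it comes from.

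On the survey date, it is fair that the enrolment-based date appears only in a parenthesis and has no window. But Section 3 applies it to all participants, which covers controls and early stoppers. No text gives the arms different clocks, and there is no evidence of bias.

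**Conclusion.** No change to the plan is needed. The time-point label in Section 9 is a clerical slip. There are no surveys at programme end and one after baseline, so the named tests can only use change from baseline to about 3 months after the programme, which is what A2b specifies. Correcting the label would alter no estimate, error rate or sample size.

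The survey date is a fair trade-off. Section 3 already supplies a date usable in both arms, and the two ways of stating it agree for a programme ending about 8.7 weeks after enrolment. A strict enrolment-based rule would align the arms on time since enrolment but loosen the link to A2b's 3-month post-programme time point, with 9.7 to 17.7 weeks since the last session under the assumed lags.

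This rests on two conditions. The first is that the schedule stays at two surveys; if the sponsor did intend a programme-end survey, the schedule itself would be incomplete, but nothing in the documents points to one. The second is that the lags from enrolment to first session are assumptions. They affect only the survey-date point and not the conclusion about the tests.
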